9.7.1. Adverse Events

Clinical and laboratory AEs will be coded using the most current version of MedDRA®. The severity will be graded according to the Common Terminology Criteria for Adverse Events (CTCAE) Version 5.0. The number of subjects experiencing treatment emergent adverse events (TEAEs) and number of TEAEs will be summarized by dosing level using frequency counts. Injection site reactions and SAEs will be tabulated. All safety data will be listed by subject. In addition, a list of AEs leading to discontinuation of study prematurely will be provided.

9.7.2. Laboratory Evaluation

Graded laboratory abnormalities will be defined according to the Common Terminology Criteria for Adverse Events (CTCAE) Version 5.0. All clinical laboratory results and their change from baseline will be summarized by dosing level and at scheduled visits. Incidence of treatment-emergent laboratory abnormalities, defined as values that increase at least one toxicity grade from baseline at any time post baseline will be summarized by dosing level. Laboratory abnormalities will also be included in a data listing. A shift table describing out-of-normal range shifts may be provided for clinical laboratory results.

9.7.3. Other Safety Evaluations

Descriptive statistic will be generated to summarize data for physical examination findings, concomitant medications, and medical history. Concomitant medications will be coded using MedDRA® Version 24.1. The number and percentage of patients taking concomitant medication will be summarized.

12-lead ECGs and vital signs measurements will be listed by subject and summarized by incidence of events/abnormalities or descriptive statistical summaries (eg, n, mean, SD, median, Q1, Q3, minimum, and maximum), as appropriate.

9.7.4. PK and Immunogenicity Analysis

SBT77701 CAR transgene level in peripheral blood and PK parameters will be listed and summarized using descriptive statistics. Relevant PK parameters (T_{max}, C_{max}, AUC₀₋₂₈, C_{last}) will be determined using standard non-compartmental methods.

Immunogenicity data will be listed by subject. The proportion of subjects with a positive anti-drug antibody result will be summarized over time and by dosing level. Proportion of subjects with at least one positive result post dosing will be summarized.

9.7.5. Exploratory Biomarker Analysis

Exploratory analyses may be performed to enhance the understanding of the biological effects, the mechanism of action, or safety of SBT77701. Exploratory analyses will include but will not be limited to the evaluation of the association of each biomarker or combination of biomarkers with clinical outcomes, the identification of molecular and/or phenotypic signatures associated with CAR signaling pathways and assessment of the CAR T_{reg} immunophenotype following dosing with SBT77701.

10. REGULATORY, ETHICAL AND LEGAL OBLIGATIONS

10.1. Ethical Considerations

It is the responsibility of the Principal Investigator to assure that the study is conducted in accordance with the study protocol, FDA regulations, ICH-GCP guidelines, applicable laws and regulations, and the Declaration of Helsinki.

10.2. Institutional Review Board (IRB) and Regulatory Approval

The Principal Investigator must inform, and obtain approval from, the IRB for the conduct of the study at the study site, the protocol, the ICF, any other written information that will be provided to the subjects and any advertisements that will be used. The Sponsor must approve the ICF and all subject recruitment materials before they are submitted to the IRB for approval. Written approval of the protocol and the ICF by the IRB must be obtained prior to recruitment of subjects into the study and shipment of study drug. The written approval of the IRB will be retained as part of the study file, and a copy will be provided to Sponsor.

Any change to the protocol requires a written protocol amendment. Proposed amendments to the protocol or any of the other aforementioned documents must be discussed with the Sponsor, and then submitted to the IRB/IEC for approval. Amendments may be implemented only after a copy of the local IRB approval letter has been transmitted to the Sponsor. Amendments that are intended to eliminate an apparent immediate hazard to subjects may be implemented prior to receiving Sponsor or IRB approval. However, in this case, the Sponsor's medical monitor and the IRB must be notified immediately, and IRB approval must be obtained as soon as possible after implementation.

The Principal Investigator will be responsible for ensuring that an annual update is sent to the IRB to facilitate its continuing review of the study and that the IRB is informed of the end of the

study. Copies of the update, subsequent approvals and the final notification letter must be sent to the Sponsor.

10.3. Institutional Biosafety Committee (IBC)

The Principal Investigator will be responsible for ensuring that the appropriate Institutional Biosafety Committee (IBC) has reviewed and approved the protocol and any other required materials prior to initiating the study if required per institutional policy.

An institution must follow the NIH Guidelines if it receives any funding from the NIH for research involving recombinant or synthetic nucleic acid molecules. Although the Sponsor does not receive any NIH funding for research involving recombinant or synthetic nucleic acid molecules; nonetheless, the Sponsor chooses voluntarily to comply. The Sponsor recognizes that following the NIH Guidelines promotes the safe and responsible practice of this research and gives the public confidence that the Sponsor is attending to important safety matters.

10.4. Insurance and Financial Disclosure

The Sponsor has obtained an insurance policy covering, in its terms and provisions, its legal liability for certain injuries caused to subjects arising out of this research performed strictly in accordance with the study protocol as well as with applicable law and professional standards.

Financial Disclosure statements for study personnel listed on the Form FDA 1572 will be handled in a separate agreement apart from the protocol, kept on file and submitted as applicable with any subsequent license application.

10.5. Essential Documentation Requirements

The Sponsor will collect from the study site the required essential regulatory documents per FDA regulations and ICH guidance prior to shipment of the study drug to the site.

10.6. Informed Consent

It is the Principal Investigator's responsibility to obtain written informed consent from each subject after adequate explanation of the objectives, methods, anticipated benefits, and potential risks of the study and before any study procedures are commenced. The subject should be given a copy of the ICF in their native language. The informed consent process should be recorded in the source documentation. The original copy of the signed and dated ICF must be retained in the study site's records and is subject to inspection by representatives of the Sponsor, contract research organization (CRO), or representatives from regulatory agencies.

10.7. Subject Privacy

The Principal Investigator must ensure that each subject's privacy is maintained. On the CRF or other documents submitted to the Sponsor, subjects will be identified by a subject study number only. Documents that are not submitted to the Sponsor (eg, ICFs) should be kept in a strictly confidential file by the Principal Investigator.

The Principal Investigator shall permit representatives of the Sponsor, CRO, regulatory agencies and IRB/IECs to review and audit the portion of the subject's medical record that is directly

related to the study. As part of the required content of informed consent, the subject must be informed that his/her records will be reviewed in this manner.

10.8. Study Record Retention and Storage

The Principal Investigator must retain a comprehensive and centralized filing system of all study-related documentation that is suitable for inspection by representatives of the Sponsor, CRO, IRB/IEC, and regulatory authorities.

The Principal Investigator will retain all records required to be maintained under 21 CFR § 312.62 for a period of 2 years following the date a marketing application is approved for SBT777101 for the indication for which it is being investigated. If no application is to be filed or if the application is not approved for such indication, the Principal Investigator will retain these records until 2 years after the investigation is discontinued and the US FDA or applicable regulatory authorities are notified.

The Principal Investigator must retain the protocol, amendments, IRB approvals, copies of the Form FDA 1572, signed and dated ICFs, medical records, original reports of test results, all other source data, eCRFs, drug accountability records, all correspondence and any other documents pertaining to the conduct of the study.

Documents should be stored in such a way that they can be accessed/data retrieved at a later date. Consideration should be given to security and environmental risks.

No study document will be destroyed without prior written agreement between the Sponsor and the Principal Investigator. If the Principal Investigator moves, withdraws from the study or retires, the responsibility for maintaining the records may be transferred to another person who will accept responsibility. Notice of transfer must be made to and agreed by the Sponsor. Further, should the Principal Investigator wish to move the study records to another location, prior written agreement must be obtained from the Sponsor.

10.9. Disclosure of Information

The contents of this protocol, information concerning the study, patent applications, processes, scientific data obtained during the study, and other pertinent information is Sponsor's confidential information and remains the property of the Sponsor. The Principal Investigator may use this information for the purposes of the study only and will not disclose such information without the Sponsor's written consent.

It is understood by the Investigator that the Sponsor will use information developed in this clinical study in connection with the development of SBT777101 and, therefore, may disclose it as required to other clinical investigators and to regulatory agencies. In order to allow the use of the information derived from this clinical study, the Investigator understands their obligation to provide complete test results and all data developed during this study to the Sponsor.

Verbal or written discussion of results prior to study completion and full reporting should only be undertaken with the prior written consent of the Sponsor.

10.10. Publication

The Sponsor plans to publish the results of the study as a whole once all subjects have completed the study and the study has been analyzed.

The Principal Investigator may not submit the data or results of the study for publication or present such data or results without the prior written consent of the Sponsor. Detailed obligations regarding the publication or presentation of any results, data, or other information generated or created in relation to the study shall be set out in the agreement between the study site and the Sponsor, as appropriate.

The Clinical Trial Agreement will detail the procedures for publications. Authorship of any publications resulting from this study will be determined on the basis of the Uniform Requirement for Manuscripts Submitted to Biomedical Journals (International Committee of Medical Journal Editors).

11. ADMINISTRATIVE OBLIGATIONS

11.1. Source Data

Original documents, data, records (eg, clinic records, laboratory notes, memoranda, subject diaries or evaluation checklists, pharmacy dispensing records, recorded data from automated instruments, copies or transcriptions certified after verification as being accurate and complete, microfiches, photographic negatives, microfilm or magnetic media, X-rays, subject files, and records kept at the pharmacy, at the laboratories, and at medico-technical departments involved in the clinical study) and all relevant sections of the subject's medical records and all other data collection made specific to this study constitute source documents.

The completed eCRF is not a source document. The Principal Investigator/study site will permit study-related monitoring, audits, IRB/IEC review and regulatory inspection by providing direct access to source documents.

11.2. Data Collection

The Principal Investigator will be responsible for maintaining accurate and adequate case records (source documents) from which data will be electronically transcribed (or if electronically captured [EDC] source data, transferred) to eCRFs designed to record data pertinent to this study and transferred to the Sponsor. All relevant observations and data related to the study will be so recorded. This will include medical and medication history, physical examinations, a checklist of inclusion and exclusion criteria, investigational treatment administration, and a record of sample collection, clinical assessments, AEs, and final evaluation. The clinical site Clinical Research Associate (CRA), site monitor or equivalent, will review all eCRFs and compare data to that contained in clinic notes and subjects' source documents/medical records.

Data collected regarding each subject will be entered into the eCRF. The Investigator will be responsible for the timeliness, completeness, and accuracy of the information and data entered into the eCRFs.

11.3. Monitoring

It is understood that CRAs, monitors, and any authorized personnel contracted by Sponsor may contact and visit the Principal Investigator and the study site, and that they will be allowed to inspect the various records of the study on request (eCRFs and other pertinent data), provided that subject confidentiality is maintained, and that the inspection is conducted in accordance with local regulations.

It is the monitor's responsibility to inspect the CRFs at regular intervals throughout the study to verify adherence to the protocol, the completeness, accuracy and consistency of the data, and adherence to GCP guidelines.

The Principal Investigator agrees to cooperate with the monitor to ensure that any problems detected during the course of these monitoring visits are resolved.

11.4. Quality Control and Quality Assurance

The Sponsor or its designee will perform quality control and quality assurance checks of all clinical studies that it sponsors according to its internal procedures. Before the enrollment of any subject in this study, the Sponsor personnel will review and provide training as needed to the Investigator, Sub-Investigators, and study site personnel regarding the following: protocol, IB, CRFs and procedures for their completion, informed consent process, and procedures for reporting SAEs. Site visits will be performed by Sponsor's CRA or designee periodically throughout the study. During these visits, information recorded on the CRFs will be reviewed against source documents, and requests for clarification or correction may be made. The CRFs will be reviewed by the CRA for safety information, completeness, accuracy, and logical consistency. Requests for clarification or correction will be sent to Investigators via data queries.

A Safety Monitoring Committee will periodically review safety data (e.g., AEs and SAEs, laboratory data) as the clinical trial is ongoing. A Quality Assurance representative of the Sponsor may audit the study. All necessary data and documents will be made available for inspection.

11.5. Site Audits and Regulatory Inspections

Periodically, the Sponsor or its authorized representatives audit clinical investigative sites as an independent review of core trial processes and documents to determine whether these activities were conducted, and data were recorded, analyzed, and accurately reported according to the protocol, GCP guidelines of the ICH, and any applicable regulatory requirements. A regulatory authority, an IEC or an IRB may visit the site to perform audits or inspections, including source data verification. The Investigator should contact the Sponsor and designee immediately if contacted by a regulatory agency, an IEC or an IRB about an inspection.

13. APPENDICES

APPENDIX A. SCHEDULE OF ASSESSMENTS: SCREENING AND PRE-TREATMENT PERIODS

	Screening	Pre-Treatment					
Study Week	-8 to -7	-6 to -1					
Study Day (visit window)			-10 to -4				
Procedure							
Informed consent	•						
Assign Allocation Number (Subject ID)	•						
Eligibility criteria	•		•				
Demographics	•						
Medical history	•	•	•				
Prior/Concomitant medications	•	•	•				
Vital signs	•	•	•				
Full physical exam	•						
Directed physical exam			•				
Height	•						
Weight	•		•				
12-lead triplicate ECG	•						
Chest X-ray	•						
Assessment of synovitis (clinical and/or ultrasound)	•	•	•				
Joint evaluation for biopsy	•						
Synovial biopsy for tissue ^a		•					
Synovial fluid collection ^a		•					
Vein assessment	•						
Apheresis		• b					
Infectious disease serology ^c	•						
TB screening ^c	•						
Serum pregnancy test	•		•				
Lipid tests ^c			•				
Coagulation ^c	•		•				
Hematology ^c	•		•				
Clinical chemistry ^c	•		•				
Urinalysis ^c	•		•				
Markers of inflammation			•				
CRP	•		•				
Joint count assessment (28 SJC and 28 TJC)			•				
Joint count assessment (66 SJC and 68 TJC)	•						
Physician VAS	•		•				
Subject VAS (global and assessment of pain)	•		•				
HAQ-DI	•		•				
FACIT-F			•				

	Screening	Pre-T	reatment
Study Week	-8 to -7	-6	to -1
Study Day (visit window)			-10 to -4
Procedure			
Blood samples for PK (ddPCR)			•
Blood sample for cellular immunogenicity			•
Blood sample for ADA			•
Blood sample for exploratory inflammatory markers			•
Blood sample for ACPA/RF			•
Blood sample for VICM			•
Blood samples for exploratory biomarkers			•
Blood samples for RCL			•
Adverse events d	•	•	•

ACPA = anti-citrullinated protein antibody; ADA = anti-drug antibody; APH = apheresis; CRP = C-reactive protein; ddPCR = droplet digital polymerase chain reaction; ECG = electrocardiogram; FACIT-F = Functional Assessment of Chronic Illness Therapy – Fatigue; HAQ-DI = health assessment questionnaire disability index; PK = pharmacokinetic; RCL = replication competent lentivirus; RF = rheumatoid factor; SJC = swollen joint count; TB = tuberculosis; TJC = tender joint count; UV = unscheduled visit; VAS= visual analogue score VICM = citrullinated and MMP degraded vimentin fragment

- ^a Synovial biopsy and/or synovial fluid collection during the Pre-treatment period should be performed after enrollment and at least one week prior to the planned dosing visit.
- ^b Apheresis should be scheduled and performed as soon as possible once screening eligibility is confirmed and the subject enters the Pre-Treatment period. The synovial biopsy should be done after apheresis.
- ^c Tests included in laboratory assessments are described in protocol Appendix C. Fasting glucose should be collected at the pre-treatment visit and as clinically indicated.
- ^d After informed consent has been obtained but prior to initiation of study drug, only SAEs caused by a protocol-mandated intervention should be reported.

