Methods:	Safety data will be listed by subject and summarized by dosing level and overall.
	Clinical and laboratory AEs will be coded using the most current version of MedDRA®. The severity will be graded according to the Common Terminology Criteria for Adverse Events. The number of subjects experiencing treatment emergent adverse events (TEAEs) and number of TEAEs will be summarized by dosing level using frequency counts. Infusion site reactions and SAEs will be tabulated. All safety data will be listed by subject. In addition, a list of AEs leading to discontinuation of study prematurely will be provided.
	Listings of individual subject laboratory results will be provided. All clinical laboratory results and their change from baseline will be summarized by dosing level and at scheduled visits and for the corresponding change from baseline (Day 1). The incidence of treatment-emergent laboratory abnormalities will be summarized by dosing level. Laboratory abnormalities will also be included in a data listing.
	Sample Size:
	The sample size in this study was not selected based on statistical considerations but to determine preliminary safety, tolerability, PK, PD, and preliminary clinical activity of SBT777101 subjects with active RA.
	Up to 18 subjects will be enrolled into dose escalation cohorts. Up to 18 additional subjects may be added in optional backfill cohorts.

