9.4. Endpoints

9.4.1. Primary Endpoint

To evaluate and characterize the safety and tolerability of SBT777101:

- Incidence, nature and severity of AEs
- Incidence and nature of DLTs
- Changes from baseline in clinical laboratory tests, 12-lead ECG parameters and targeted vital signs

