APPENDIX B. SCHEDULE OF ASSESSMENTS: BASELINE AND SAFETY FOLLOW-UP PERIOD

	Safety Follow Up														UV	\mathbf{E}	
Study Week Study Day (visit window)	1					2	3 4		6 8		10	12	24	36	48/ES		T
	1	2	4 or 5	7 ±1	11 ±1	14 ±2	21 ±2	28 ±2	42 ±2	56 ±2	70 ±2	84 ±3	168 ±7	252 ±7	336 ±7		
Procedure		•		•				•	•				•	•			
SBT777101 administration	•																
Overnight stay/acute safety monitoring	•																
Patient self-temperature monitoring	•	•	•	•	•	•	•	•	•	•	•	•	•	•	•	•	•
Patient check-in (phone call, text etc) ^a		•	•	•													
Vital signs ^b	•	•	•	•	•	•	•	•	•	•	•	•	•	•	•	•	•
Adverse events ^c	•	•	•	•	•	•	•	•	•	•	•	•	•	•	•	•	•
Prior/Concomitant medications	•	•	•	•	•	•	•	•	•	•	•	•	•	•	•	•	•
Full physical exam				•				•		•					•		•
Directed physical exam	•	•	•		•	•	•		•		•	•	•	•		•	
Weight										•					•		•
12-lead triplicate ECG				•		•									•	•	•
Synovial biopsy for tissue								● ^{d,e}									•
Synovial fluid collection								●d,e				●d,e,f					•
Assessment of synovitis (clinical and/or ultrasound)								•				•					•
Urine pregnancy test	•											•	•		•		•
Lipid tests ^g															•		
Coagulation ^g													•		•		
Hematology ^g		•	•	•	•	•	•	•	•	•	•	•	•	•	•	•	•
Clinical chemistry ^g		•	•	•	•	•	•	•	•	•	•	•	•	•	•	•	•
Urinalysis ^g										•				•	•		•
Markers of inflammation h																•	
CRP		•		•		•	•	•	•	•	•	•	•	•	•	•	•
Joint count assessment (28 SJC/28 TJC)						•		•		•			•		•		•
Joint count assessment (66 SJC/68 TJC)												•					
Physician VAS						•		•		•		•	•		•		•
Subject VAS (global and assessment of pain)						•		•		•		•	•		•		•
HAQ-DI						•		•		•		•	•		•		•
FACIT-F													•		•		•
Blood samples for PK (ddPCR) i		•	•	•	•	•	•	•	•	•	•	•	•	•	•	•	•
Blood sample for cellular immunogenicity												•			•	•	•

FINAL Confidential

Version 1.0, 18-MAY-2022 Page 72 of 92

		Safety Follow Up				UV	ET										
Study Week			1			2	3	4	6	8	10	12	24	36	48/ES		
Study Day (visit window)	1	2	1 0 7 5	7	11	14	21	28	42	56	70	84	168	252	336		
	1	Z	4 or 5	±1	±1	±2	±2	±2	±2	±2	±2	±3	±7	±7	±7		
Procedure																	
Blood sample for ADA										•					•	•	•
Blood sample for exploratory inflammatory markers		•		•		•	•	•	•	•	•	•	•	•	•	•	•
Blood sample for ACPA/RF						•	•	•	•	•	•	•	•	•	•		•
Blood sample for VICM				•		•	•	•	•	•	•	•	•	•	•		•
Blood samples for exploratory biomarkers		•	•	•	•	•	•	•	•	•	•	•	•	•	•	•	•
Blood samples for RCL												•	•		•		

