ACPA = anti-citrullinated protein antibody; ADA = anti-drug antibody; CRP = C-reactive protein; ddPCR = droplet digital polymerase chain reaction; ECG = electrocardiogram; ES = End of Study; ET = early termination; FACIT-F = Functional Assessment of Chronic Illness Therapy – Fatigue; HAQ-DI = health assessment questionnaire disability index; PK = pharmacokinetic; RCL = replication competent lentivirus; RF = rheumatoid factor; SJC = swollen joint count; TJC = tender joint count; UV = unscheduled visit; VAS= visual analogue score VICM = citrullinated and MMP degraded vimentin fragment

Note: On Day 1, all assessments should be performed prior to dosing, unless otherwise specified.

- ^a Subjects should be contacted daily by the site (e.g by phone or text) following discharge through Day 7.
- ^b Vital signs must be measured approximately 15 minutes prior to infusion, then approximately every 15 minutes during the infusion.
- ^c After informed consent has been obtained but prior to initiation of study drug, only SAEs caused by a protocol-mandated intervention should be reported. After initiation of study drug, all AEs will be reported until the end of the study. After this period, the Sponsor should be notified if the investigator becomes aware of any SAE that is believed to be related to prior study drug treatment
- ^d The synovial biopsy/fluid collection can be performed at or up to 1 week after the scheduled assessment visit.
- ^e The timing of the synovial biopsy and/or synovial fluid collection in may be changed based on evaluation of data from the first dose escalation cohort.
- $^{\rm f}$ The synovial biopsy sample/fluid collection at Week 12 and at the ET visit is optional.
- g Tests included in laboratory assessments are described in protocol Appendix C.
- ^h A sample to test for markers of inflammation should be collected within 30 minutes of the onset of a suspected adverse event of infection or CRS.
- ⁱ The PK sample collected on study Day 2 should be collected at approximately the same time of day that the infusion of study drug took place on study Day 1 (+/- 1 hour). An unscheduled PK sample should be collected within 30 minutes of a suspected infusion related reaction adverse event.

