APPENDIX C. CLINICAL LABORATORY TESTS

The tests detailed in Table 4 will be performed at the times specified in the SoA (Appendix A and Appendix B).

Additional tests may be performed at any time during the study as determined necessary by the Investigator or required by local regulations.

Table 4: Protocol-Required Safety Laboratory Tests

Laboratory Tests	Parameters						
Hematology	Platelet count		RBC indices	RBC indices:		White blood cell	
(CBC with diff, RBC indices)	Red blood cell (RBC count	C)	Mean corpuscular volume (MCV)		diff	BC) count with erential:	
	Hemoglobin		Mean corpus hemoglobin			trophils nphocytes	
	Hematocrit		%Reticulocy	` /	_	nocytes	
						inophils	
						ophils	
Clinical chemistry (comprehensive metabolic panel including transaminases and bilirubin)	Blood urea nitrogen (BUN)	Potassium		Aspartate aminotransferase (AST)/serum glutamic- oxaloacetic transaminase (SGOT)		Total and direct bilirubin	
	Creatinine	Sodi	um	Alanine aminotransferas (ALT)/serum glutamic-pyruv transaminase (SGPT)		Total protein	
	Glucose (fasting at the pre- treatment visit and as clinically indicated)	Calci	ium	Alkaline phosphatase		HbA1c (only for subjects with a history of glucose intolerance, pre-diabetes or diabetes)	
	Chloride	Bicar	rbonate	Albumin			
Lipid tests	LDL	•		Total cholester	ol		

 Table 4:
 Protocol-Required Safety Laboratory Tests (Continued)

Laboratory Tests	Parameters			
Serology	Hepatitis B surface antigen [HbsAg],	Hepatitis C virus antibody		
Tuberculosis screening	Quantiferon Gold			
Coagulation	PT	INR		
	aPTT			
Urinalysis	Specific gravity pH, glucose, protein, blood, ketones, by of Microscopic examination (if blood or pro	1		
Pregnancy testing	Highly sensitive [serum or urine] human chorionic gonadotropin (hCG) pregnancy test (for women of childbearing potential)			
Other screening tests	Follicle-stimulating hormone (FSH) and post-menopausal)	estradiol (as needed in women reported as		

Investigators must document their review of each laboratory safety report.

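### Glucose must be fasting before dosing but has no set fasting state at the post-dose visits, so its change from baseline is confounded by fasting state, probably upward

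*Protocol*

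**What the plan says.** Two places set the fasting rule. The laboratory footnote to Appendix A reads "Fasting glucose should be collected at the pre-treatment visit and as clinically indicated", and Table 4 in Appendix C lists "Glucose (fasting at the pre- treatment visit and as clinically indicated" among the chemistry tests. In Appendix A, chemistry is marked at screening and at Day -10 to -4, so the latter is the pre-treatment visit to which the rule applies.

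Appendix B marks chemistry at Days 2, 4 or 5, 7, 11, 14, 21, 28, 42, 56, 70, 84, 168, 252 and 336, which makes 14 scheduled post-dose visits, plus unscheduled and early-termination visits. Day 1 has no mark. The footnote to that row says only "Tests included in laboratory assessments are described in protocol Appendix C" and adds no fasting rule of its own.

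Section 9.4.1 includes in the primary endpoint "Changes from baseline in clinical laboratory tests, 12-lead ECG parameters and targeted vital signs". Section 9.7.2 states: "All clinical laboratory results and their change from baseline will be summarized by dosing level and at scheduled visits". It also counts rises of at least one toxicity grade from baseline and allows for a shift table. Glucose is not exempted. The synopsis, under statistical methods, refers to the "corresponding change from baseline (Day 1" value as the reference.

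**The concern.** A fasting glucose and a glucose drawn at an arbitrary time of day are different quantities. If the reference sample is fasting and some later samples are not, the difference contains a meal effect as well as any effect of treatment or time. The trial is open-label and single-arm, so no concurrent control carries the same meal effect and lets it be subtracted.

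Glucose is not an idle analyte here. Oral corticosteroids are permitted, with temporary increases during follow-up (Table 2), and HbA1c is collected in subjects with a history of glucose intolerance, pre-diabetes or diabetes. A rise in the glucose table could be read as a drug or steroid effect when it reflects sampling conditions, or a real change could be dismissed as a meal effect. With escalation cohorts of 3 to 6 subjects, a few non-fasting samples can move a dose-level mean. If fasting state is not captured at the draw, it cannot reliably be recovered at analysis.

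**Working it through.** The protocol states no glucose mean, standard deviation, reference range or fed-minus-fasting difference, so there is no figure to reproduce. The check compares the passages and then gives an illustration on stated assumptions.

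**Step 1. Fasting state by visit**

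| Sample | Chemistry scheduled | Fasting rule |
|---|---|---|
| Screening (Week -8 to -7) | yes | none stated |
| Day -10 to -4 | yes | fasting |
| Day 1 | no | not applicable |
| 14 visits, Day 2 to Day 336 | yes | only where there is a clinical reason |

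**Step 2. Which sample is the baseline.** The synopsis names Day 1, but no chemistry is scheduled then. Taking the last scheduled value before dosing gives the fasting Day -10 to -4 sample. This is an inference; the protocol does not say so.

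**Step 3. Expected change with no drug effect.** Let d be the mean fed-minus-fasting difference and f the share of post-dose draws that are non-fasting. With a fasting baseline, expected change = f × d. Both inputs are assumptions.

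- f = 0 (all post-dose draws fasting): 0
- f = 0.25, d = 5 mg/dL: 0.25 × 5 = +1.25 mg/dL
- f = 0.5, d = 15 mg/dL: 0.5 × 15 = +7.5 mg/dL
- f = 1, d = 30 mg/dL: +30 mg/dL

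If the screening sample were the baseline instead, and a share f0 of screening draws were non-fasting, the expected change would be (f − f0) × d. That can have either sign, because f0 is also unspecified.

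**Step 4. How often a mean rise would be seen with no drug effect.** With SD the standard deviation of the within-subject change (assumed) and n subjects, P(mean change > 0) = Φ(f × d × √n / SD). The values of n are 3 and 6 (escalation cohort sizes), 12 (6 plus a backfill of 6) and 36 (study maximum).

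| d (mg/dL) | f | SD (mg/dL) | n = 3 | n = 6 | n = 12 | n = 36 |
|---|---|---|---|---|---|---|
| 5 | 0.25 | 25 | 0.53 | 0.55 | 0.57 | 0.62 |
| 15 | 1 | 25 | 0.85 | 0.93 | 0.98 | 1.00 |
| 30 | 1 | 10 | 1.00 | 1.00 | 1.00 | 1.00 |

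For example, in the second row at n = 3: 15 × √3 / 25 = 1.04, and Φ(1.04) = 0.85.

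**Step 5. After matching.** If both samples of a pair have the same fasting state, the built-in shift is 0 and P(mean change > 0) is 0.50 for any n and SD.

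**The case against.** **Post-dose fasting is unspecified, not excluded.** A reader might infer that glucose is bound to rise at every post-dose visit. The documents do not support that. The rule allows fasting samples after dosing, nothing declares the post-dose draws to be non-fasting, and f = 0 gives no shift. This objection stands: the text supports confounding with a probable direction, not a certain rise.

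**The size rests on outside figures.** A reader might also infer that most subjects would shift above the normal range. Assuming a fasting mean of 92 mg/dL, an upper limit of 100 mg/dL and every post-dose draw non-fasting at 10 to 30 mg/dL higher, simulation puts 49% to 82% of those with a normal baseline above range at a single visit. With a quarter of draws non-fasting the share is 22% to 30%, and with none it is 13% to 20%, depending on the assumed post-dose scatter. None of these inputs is in the protocol, so the shares cannot be used as a finding.

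**Other documents may cover it.** Section 7.2.6 refers sampling procedures to the Laboratory Manual, and Section 9.7 leaves safety analysis details to the SAP. The SAP may choose the baseline record, but it cannot match on a fasting state that was never captured. The Laboratory Manual might capture it; it is not available here. The protocol does set a fasting rule itself, and sets it for one side of the comparison only.

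**The consequence is small.** This stands. Section 9.7 rules out inferential statistics on safety. Under Section 3.3 escalation rests on related adverse events of Grade 3 or higher, and Appendix E makes a laboratory value an adverse event only if it is clinically significant and needs active management. Uncontrolled diabetes is excluded. A meal effect common to all dose levels would also cancel between doses, though only if the share of non-fasting draws is the same in each cohort, which nothing secures.

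**Conclusion.** The point holds as a confounding of glucose change from baseline with fasting state. The pre-dose sample most likely to serve as baseline must be fasting, the 14 scheduled post-dose samples need not be, and the protocol does not require the state to be recorded. The bias is probably upward. Its size cannot be computed from the protocol: it is 0 if all post-dose draws are fasting, and +1.25 to +30 mg/dL over assumed differences of 5 to 30 mg/dL and non-fasting shares of 25% to 100%. The conclusion rests on the inference that the Day -10 to -4 sample is the baseline, because the named Day 1 has no chemistry. The impact is minor: one analyte in a descriptive summary, although that summary belongs to the primary endpoint. Sample size, error rates and the escalation rule are not affected.

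**What to change.** 1. Record fasting status with every glucose value, including screening, on the eCRF or laboratory requisition.
2. In Section 9.7.2, summarize glucose change and shifts only between samples of the same recorded fasting status. Alternatively, apply the same fasting condition at the baseline sample and at the visits used for change from baseline.
3. Name the pre-dose sample that serves as laboratory baseline, and reconcile this with the synopsis.

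The screening glucose can serve as a non-fasting reference only if its own status is recorded. It is also old: screening is at Week -8 to -7, and Section 7.1.2.4 allows reassessment for dosing up to 6 months after enrollment.

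The cost is one data field, one or two sentences in Section 9.7.2, and fewer matched pairs for glucose. The field has to be in place before samples are drawn.
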